Rejuvesol® Washed RBC in Sickle Cell Patients Requiring Frequent Transfusions
Research Summary

**Rejuvesol® Washed RBC in Sickle Cell Patients Requiring Frequent
Transfusions**

NCT02731157

Document Date: 2017-02-26

Rejuvesol® Washed RBC in Sickle Cell Patients Requiring Frequent Transfusions **Research Summary**

Protocol Title: Rejuvesol® Washed RBC in Sickle Cell Patients Requiring Frequent Transfusions

Purpose of the Study – The long-term goal of reducing morbidity and increasing treatment intervals for chronically transfused patients, the objective of this study is to test the feasibility of the novel application of red blood cell (RBC) rejuvenation to chronic transfusion in sickle cell disease (SCD) and the potential benefit in terms of RBC longevity, prothrombotic microparticle (MP) formation, and oxygen (O₂) delivery capacity of transfused RBCs.

The purpose of this study is to:

1. To demonstrate that Rejuvenation improves *in vivo* RBC survival.

We hypothesize that the loss of HbA over a transfusion interval will be reduced after a transfusion treatment with rejuvenated compared to standard RBCs.

This will allow prolonging transfusion intervals to maintain the same %HbA target.

2. To determine whether Rejuvenation reduces *in vivo* RBC microparticles.

We hypothesize that *in vivo* RBC-MP counts and RBC/RBC-MP-mediated thrombin generation before transfusion therapy will be lower after a prior treatment with rejuvenated compared to standard RBCs (“trough level”). Similarly, RBC-MP counts and RBC/RBC-MP-mediated thrombin generation will be lower immediately after transfusion therapy with rejuvenated compared to standard RBCs (“peak level”). This will minimize the contribution of transfusion therapy to the pre-existing, prothrombotic MP burden.

3. To demonstrate optimal *in vivo* O₂ delivery capacity after Rejuvenation

We hypothesize that, compared to standard RBCs, transfusion of rejuvenated blood will not reduce the p50 of patients’ blood. A high p50 is a compensatory mechanism to maintain tissue O₂ delivery in SCD, since standard RBCs have a low p50 from 2,3-DPG loss.

Background & Significance – SCD is a group of inherited RBC disorders that affects approximately 100,000 SCD patients in the United States and millions worldwide, making it a major national and international health concern. Patients with SCD that require RBC therapy carry the burden of approximately monthly transfusions to maintain their health due to clearance of transfused cells. In contrast to other medical treatments for SCD complications, repeated RBC therapy via RBC-ST or RBC-XT is considered for those with the most severe disease manifestations. These patients have often suffered or have an elevated risk of developing SCD complications such as stroke, transient ischemic attack, acute chest syndrome, priapism, or persistent chronic pain. While beneficial, transfusion is also associated with potential risks and adverse effects, including immune hemolysis, RBC alloimmunization, iron overload, transfusion reactions, and infection with bacteria, viruses, and parasites are all potential risks of transfusion; therefore maximizing the benefit and minimizing the risk of each transfusion is necessary. RBC transfusion was approved on the basis of short-term quantitative parameters, including <1% hemolysis in the unit at time of infusion and an *in vivo* recovery >75% of

Rejuvesol® Washed RBC in Sickle Cell Patients Requiring Frequent Transfusions **Research Summary**

transfused cells 24 hours after infusion. There was no regard for the RBC quality, longer-term *in vivo* survival kinetics, burden of RBC byproducts with repeated transfused doses, or tissue oxygenation capacity. Subsequent research has demonstrated that RBCs exhausted by refrigerated storage are structurally and functionally abnormal. These cells are more rigid, less tolerant of stress, form increased pathogenic *ex vivo* RBC-MPs, and abnormally adhere to the vascular endothelium.^{1,2,6,20} Intracellular ATP levels decrease during storage and can impair the ability of RBCs to effect local vasodilation in hypoxic microcirculatory environments to promote O₂ delivery.^{24,25} Furthermore, ATP losses decrease the function of vital intracellular ATP-dependent enzymes, such as the flippases that maintain normal membrane phospholipid asymmetry.²⁶ Stored RBCs are also depleted of 2,3-DPG and have lower p50, thus are less effectively able to transport and release O₂ where it is needed in the tissues.³ Once transfused, these altered RBCs are cleared from circulation and produce additional burdens of RBC byproducts and RBC-MPs already present in SCD patients.⁴⁻⁶ Rejuvenation of stored RBCs in the Blood Bank is a FDA-approved process that improves several cell parameters that are directly relevant to SCD pathophysiology, including RBC recovery, RBC-MP burden, *in vivo* RBC-MP formation, ATP and 2,3-DPG levels, p50, microcirculatory oxygenation, membrane deformability, and vascular endothelial adhesion.^{2,3,14-20} Surprisingly, benefits of RBC rejuvenation for transfusion in the SCD population specifically have not been explored. We postulate that RBC rejuvenation increases the *in vivo* survival of transfused RBCs, decreases pathogenic RBC-M formation *in vivo*, and can improve *in vivo* tissue oxygenation via normalization of p50.

University of Colorado-Denver (UC-Denver). [name] has extensive experience analyzing the metabolic changes that occur during RBC storage^{34,35}, and is interested in identifying the biochemical differences between RBCs of sickle-cell patients receiving rejuvenated transfusions compared to standard transfusions. As such, we propose an external specimen repository, to be stored securely at UC-Denver under the supervision of [name], which will be used to conduct future research that is unspecified at this time but will generally involve metabolomic analyses of subject RBCs. Investigators at Duke will contribute only leftover blood samples to this repository, and subjects will be given the option to opt-in or opt-out of this repository. Subjects will not receive additional needlesticks for this repository and no additional blood will be drawn. All biological samples will be de-identified and no personnel outside of DUHS will be provided with information that can be used to identify subject samples. All sample transfer will occur within the context of a pending materials transfer agreement, and [name] will obtain IRB approval or waiver from his institution for this repository.

Design & Procedures – This is a pilot study. In this prospective, single blind, cross-over clinical trial, patients with sickle cell disease will receive either rejuvenated (R) or standard (S) RBCs with each treatment over a 6-treatment period as follows to maximize detection of any signal: SRR|RSS. Each patient will receive 1 transfusion per treatment. Each transfusion consists of 2 units of RBCs or RBC apheresis exchange consisting of approximately 5 units of RBCs. Treatment 1 after enrollment the patient will receive the standard RBC's (in all units) Treatment 2 and treatment 3 the patient will receive the RBCs treated with Rejuvesol (in the last 4 units). The patient then crosses over to the RSS arm. Treatment 4 the patient receives Rejuvesol treated RBCs (in the last 4 units). Treatments 5 and 6 the patient receives standard RBCs (in all units). For patients receiving RBC-XT, only the final 4 RBC units used in the treatment will be rejuvenated as they are the most likely to persist in circulation following treatment completion. The Duke site ([name]) will enroll 4 chronically transfused patients receiving RBC-ST (2 units each month) or RBC-XT (approximately 5 units each month). Total patient enrollment at Duke is expected to be 4 subjects and will be treated as a single site pilot study.

Patients at Duke undergo RBC-ST with 2 units or RBC-XT with approximately 5 units every 4-6 weeks. This established care pattern and current medications will be recorded but not altered. Only the RBC units will be modified.

RBCs provided by the Blood Bank

All patients will receive crossmatch-compatible leukoreduced RBCs that have been phenotypically matched for at least ABO, D(Rh), C, E, and Kell antigens. For sessions in which standard units are used, no additional manipulations will be performed. For sessions in which rejuvenated units are needed, rejuvenation will be performed with Rejuvesol® RBC Processing Solution (Citra Labs, LLC, Braintree, MA) per manufacturer's protocol.³⁰ Briefly, RBC units are incubated with rejuvenating solution for 1 hr at 37 C in the blood bank under the supervision of co-director [name], washed with saline in a C.A.T.S. (Fresenius Kabi AG; Bad Homburg, Germany), and suspended in 0.9% saline/0.2% dextrose for transfusion. The C.A.T.S. is

Rejuvesol® Washed RBC in Sickle Cell Patients Requiring Frequent Transfusions **Research Summary**

an intra-operative cell-salvage device maintained by the Biomedical Engineering Department and routinely used in the ORs. The C.A.T.S. is FDA-approved for the preparation of washed RBC units, and thereby meets Rejuvesol® manufacturer's specifications for the required washing step. Due to logistical challenges, the wash procedure will be performed at the bedside by study personnel specifically trained in the use of the C.A.T.S. apparatus, and the C.A.T.S. apparatus will be maintained using standard blood bank QC procedures. Flowsheets designed in conjunction with the blood bank will be used during these wash procedures to maintain the safety and integrity of the RBC units and wash process. All flowsheets and QC will be maintained in study binder and reviewed monthly by [name] of the blood bank. Consistent with AABB regulations, all units washed with the C.A.T.S device will be transfused within 4 hours.

Demographics and standard clinical and laboratory data

Demographic data include age, sex, race, height, and weight. Pre- and post-transfusion session vital signs will be recorded (temperature, heart rate, respiratory rate, blood pressure, and pulse oximetry), complete blood count with differential, peripheral blood film analysis (Advia 120; Siemens Healthcare, Malvern, PA) and HbA/S analysis routinely drawn. ABO type, RBC antibody screen, calculated patient total blood volume, calculated patient total RBC volume, and volume and storage age of RBCs transfused for each session will also be recorded.

Study specific laboratory data

With no additional blood draw time points or venipunctures, an additional 18 ml whole blood will be drawn into 4 citrated tubes and 2 EDTA tubes for RBC-MPs and p50 measurements at the time of routine blood draws pre- and post-transfusion. This means the total monthly volume of study blood is 36ml.

Specific procedures to accomplish each objective

1. Hb A/S determinations. Samples will be whole blood in EDTA. Bio-Rad Variant II HPLC system with Variant II β -Thalassemia Short Program Reorder Pack (Bio-Rad Laboratories, Inc.; Hercules, CA) will be used per manufacturer's instructions. Briefly, samples will be mixed, diluted with specific hemolyzing/wash buffer, and injected into an analytic cartridge. Absorbance will be measured at 415 nm. Background noise will be reduced with use of a second wavelength at 690 nm. Raw data will be integrated by manufacturer's software, and a chromatogram will be generated. Integrated peaks will be

assigned to manufacturer-defined windows derived from retention time of the peaks. The %Hb will be calculated by determining the area of a peak as a fraction of the total area of all Hb peaks on the HPLC chromatogram.

2: RBC-MP determinations. Samples will be whole blood in citrate. The first blood tube will be discarded to avoid contamination during venipuncture. Blood will be centrifuged at 1,500g for 10 min at 4 C. The supernatant will be carefully removed into microcentrifuge tubes, taking care not to disturb the buffy coat layer. A second centrifugation will be performed at 2,000g for 5 min to obtain platelet free plasma (PFP) to be frozen at -80 C. PFP aliquots (30 μ L) will be stained with the following markers/antibodies: 10 μ L FITC-labeled AnnexinV mixed 1:1 with Annexin binding buffer (10 mM HEPES, 140 mM NaCl, 2.5 mM CaCl2) and 2 μ L PE-labeled anti-CD235a. All markers/antibodies will be centrifuged at 20,000g x 20 min prior to use. RBCMs will be defined as Annexin+/CD235+ events. Calcium-free samples and

Rejuvesol® Washed RBC in Sickle Cell Patients Requiring Frequent Transfusions **Research Summary**

single-stained MP-free plasma samples (supernatant from normal, healthy donor PFP spun at 100,000g x 60min and stored at -80 C until use) will be used as negative controls. BD CompBeads® will be run as compensation controls per manufacturer's instructions. Stained samples will be incubated in the dark for 20 min and then further diluted with 500 μ L of Annexin binding buffer or phosphate buffered saline prior to analysis. All buffers will be filtered through a 0.1 μ m filter prior to use. CytoCount® beads will be added to each sample in equal volume as PFP (30 μ L) immediately prior to analysis to enable MP enumeration. The concentration of MPs in each sample will be calculated as follows: (MPs counted x concentration of beads) / number of beads counted. All samples will be analyzed on a Stratidigm S1000Ex (Stratidigm; San Jose, CA, USA) high-sensitivity flow cytometer equipped with a forward scatter photomultiplier tube (FSC PMT) using a side scatter (SSC) trigger and 0.1 μ m filtered sheath fluid. MP size gate for analysis will be set between 200 and 1000 nm utilizing Megamix Plus FSC/SSC® beads, which are a mixture of 900, 500, 300, 240, 200, 160 and 100 nm fluorescent beads. Event rates will be <8000 events/sec for all samples to minimize coincident events.

RBC-mediated thrombin generation determinations. Phosphatidylserine (PS) has been found to directly correlate with rate of production of meizothrombin-antithrombin (mTAT) complexes and thrombin generation on RBCs. Whole blood samples will be collected in EDTA. For positive controls, washed RBCs will be diluted to 20% hematocrit in RBC wash buffer and incubated with 10mM N-ethylmaleimide (NEM) at 37 C for 30 min. NEM-treated cells will then be washed 3 times before incubation with a 4 μ M concentration of the calcium ionophore A23187 at 37 C for 30 min. Ionophore-treated cells will be washed 3 times and diluted to 2x10⁶ cells/mL in RBC wash buffer. Similar to controls, samples will be incubated and washed but without NEM or ionophore treatment. RBCs will be detected using PE-anti-glycophorin A (CD235a). RBC PS will be measured via binding of FITC-labeled Annexin V on a FACS Canto II flow cytometry (BD Biosciences Franklin Lakes, NJ).

RBC-MP-mediated thrombin generation determinations. Whole blood samples will be collected in citrate. PFP will be prepared as described above and frozen at -80 C. The Zymuphen ELISA (Aniara Inc., West Chester, OH) is a functional assay that measures the procoagulant activity of MPs in PFP. A microtiter plate is pre-coated with annexin V-streptavidin. PS+ MPs bind to the plate and expose their phospholipid surface, allowing

pro-thrombinase complex to cleave prothrombin into thrombin. Phospholipid in the sample is the limiting factor, so there is a direct relationship between MP phospholipid concentration and thrombin generation. Thrombin generation will be measured by a specific chromogenic substrate. Thawed PFP samples and kit controls will be diluted 1:20 in the kit sample diluent and supplemented with calcium, Factor Xa (FXa), and thrombin. A calibrator curve, diluted controls and diluted samples will be added to the ELISA plate and incubated for 1 hr at 37 C. The plate will be washed five times, then 100 μ L of Reagent 1 (FXa-FVa) and 50 μ L Reagent 2 (prothrombin) will be added and incubated for 10 min at 37 C, then 50 μ L of Reagent 3 (thrombin substrate) will be added, and incubated for 3 min at 37 C. Finally, 50 μ L of stop solution will be added and absorbance read at 405 nm. Results will be calculated from the calibrator curve.

3: O₂-binding curves and P50 determinations. RBCs will be washed and PBS

Rejuvesol® Washed RBC in Sickle Cell Patients Requiring Frequent Transfusions **Research Summary**

containing DTPA. A 10% hematocrit suspension will be prepared in Krebs buffer. The RBC suspension will be placed in a specially designed, temperature- and humidity controlled rotating tonometer. RBCs will be progressively exposed to varying gas mixtures in order to produce fixed solution O₂%, typically including 2%, 5%, 8%, and 20%. After 10 min of gas mixture at each pO₂% sample will be removed from the tonometer for blood gas measurement. An Abbott i-Stat (Abbott Laboratories; Abbott Park, IL) will be used to measure pO₂ and directly measures including Hb O₂ saturation. The Hb O₂ saturation versus pO₂ curve will be constructed and p50 extrapolated for each sample. p50 results will be generated and O₂-binding curves displayed graphically.

4: Preparation of samples for external repository. Any blood remaining after the above analyses are complete will be spun to separate RBCs and plasma at 2000g for 10 minutes at 4 degrees Celsius. Once separated, plasma and RBCs will be stored in separate deidentified cryovials at -80 degrees Celsius. These specimens will be batch-shipped to [name] [name] at the University of Colorado-Denver according to the terms of the pending materials transfer agreement.

Selection of Subjects – Inclusion criteria: Adults 18 years of age and older who are undergoing frequent RBC transfusions as part of their routine care for Sickle cell disease will be approached for participation. Exclusion criteria: Patients with acute pain crisis with 2 weeks prior to enrollment. Duke expects to enroll 4 subjects for this pilot study.

Subject Recruitment and Compensation – Subjects will be identified by the Co-investigator [name] for the Sickle cell patients after review of the sickle cell transfusion schedule. All subjects are [name] patients. The consent form will be presented to the prospective subjects/parents by the physician investigator in this study or the study coordinators known to the subject/parents. Participation in the research study will not significantly alter the routine clinical management as currently practiced at Duke University Medical Center. Patients will not be compensated for participation in the research study.

Consent Process – See section 14 of the eIRB submission

Subject's Capacity to Give Legally Effective Consent – All subjects must have the capacity to give legal consent.

Study Interventions – Please refer to item 4

Risk/Benefit Assessment – It is impossible to estimate without conducting this study what the benefit or risk of participation in this study is. There are no apparent risks for subjects participating in this study. Rejuvenation is an FDA approved process and an AABB standardized procedure; furthermore pediatric patients may often receive washed units of packed red blood cells. Risks are no more than receiving a unit of PRBCs as all these products are approved. No subject will receive a transfusion specifically for the

Rejuvesol® Washed RBC in Sickle Cell Patients Requiring Frequent Transfusions **Research Summary**

purpose of this study. RBC rejuvenation will only involve units of blood that would have been used for the patient regardless of the study.

No additional blood draws will be done specifically for the study. An additional 36ml of blood (18ml pre-transfusion and 18 ml post transfusion) will be drawn with the standard of care labs..

Costs to the Subject – There is no cost to the subject for participation in this study.

Data Analysis & Statistical Considerations –Routine clinical measurements will be compared with repeated measures analysis of variance. As this is a pilot study and there is no control group, the only relevant changes to analyze will be pre- and post-procedure. Statistical data obtained (noted and described in the Design and Procedures section) will be used for future planning of a larger comparison study.

No interim analysis is planned but adverse events will be reported to the IRB as required.

1: To demonstrate that Rejuvenation improves *in vivo* RBC survival. We hypothesize that the loss of HbA over a transfusion interval will be reduced after a transfusion treatment with rejuvenated compared to standard RBCs. HbA/S determination is routinely performed pre- and post- treatments. The %HbA decrement is the current pre-treatment HbA – previous post treatment HbA in %. Our primary outcome variable will be HbA decrement per day to account for minor variability. A generalized linear model will be applied to determine whether the mean difference in HbA exceeds +/-19%. Secondary outcomes will evaluate actual HbA decrement (g/dl) with and without indexing to calculated circulating blood volume. If %HbA decrement with rejuvenated units exceeds -19% we will reject the null hypothesis and conclude that rejuvenation will permit prolonging transfusion intervals by a week to maintain the same %HbA target. Whether or not we reject the null hypothesis, these data will inform treatment effect size and prospective collection of %HbA variability can validate preliminary data strengthening future sample size estimate calculations.

2: To determine whether Rejuvenation reduces *in vivo*, RBC microparticles. We hypothesize that *in vivo* RBC-MP counts and RBC/RBC-MP-mediated thrombin generation before transfusion therapy will be lower after a prior treatment with rejuvenated compared to standard RBCs (“trough level”). Similarly, RBC-MP counts and RBC/RBC-MP-mediated thrombin generation will be lower immediately after transfusion therapy with rejuvenated compared to standard RBCs (“peak level”). These secondary outcomes will inform on effect size of rejuvenation on the immediate changes in RBC-MP counts after treatment. If reduction in RBC-MPs is augmented by rejuvenation, better efficacy of treatment could be postulated and subsequently tested, as this will minimize the contribution of transfusion therapy to the

preexisting, prothrombotic MP burden. Phosphatidylserine (PS) has been found to directly correlate with rate of production of meizothrombin-antithrombin (mTAT) complexes and thrombin generation on RBCs. The capacity of RBCs and RBC-MPs to generate thrombin could inform evaluation of future anticoagulation needs and targets. Wilcoxon Rank Sum tests will be used to compare RBC-MP counts and thrombin generation.

3: To demonstrate optimal *in vivo* O2 delivery capacity after Rejuvenation. We

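### Every patient follows the same fixed order S-R-R-R-S-S, so the rejuvenated-minus-standard difference cannot be separated from non-linear interval effects shared by the patients, yet the analysis section draws a causal conclusion from it

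*Combined protocol and SAP*

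**What the plan says.** Design & Procedures describes a prospective, single-blind cross-over in which treatment runs "over a 6-treatment period as follows to maximize detection of any signal: SRR|RSS". The bar could suggest two parallel sequences, but the text that follows gives one sequence. It starts with "Treatment 1 after enrollment the patient will receive the standard RBC's (in all units"), then rejuvenated product at treatments 2 and 3. It continues "The patient then crosses over to the RSS arm", with rejuvenated product at treatment 4, and finishes with "Treatments 5 and 6 the patient receives standard RBCs (in all units"). No alternative order, allocation method or randomisation is described. Four patients are expected, "receiving RBC-ST (2 units each month) or RBC-XT (approximately 5 units each month").

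In Data Analysis & Statistical Considerations, the primary outcome is the %HbA decrement per day, taken from one post-treatment sample to the next pre-treatment sample. The model is given only as "A generalized linear model will be applied to determine whether the mean difference in HbA exceeds +/-19" per cent; no interval term is named. The section on demographics and standard data says that "volume and storage age of RBCs transfused for each session will also be recorded", but neither variable is placed in the model.

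The analysis section opens with a limitation: "As this is a pilot study and there is no control group, the only relevant changes to analyze will be pre- and post-procedure". Its first objective then sets a rule for rejecting the null. If the threshold is passed, it would conclude that rejuvenation allows the interval to be a week longer, and in either case the data are to inform the treatment effect size.

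**The concern.** A cross-over separates treatment from time by giving different patients different orders. Here rejuvenated product always falls at treatments 2 to 4 and standard product at 1, 5 and 6. Anything that affects all patients at the same treatment number, other than a straight-line drift, is absorbed into the R-S estimate. More patients on the same order would not help, because the overlap lies in the design and is not a matter of sample size.

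Two things are at stake. The planned conclusion attributes the whole difference to rejuvenation. The effect size carried into a larger study would also inherit any bias.

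**Working it through.** **Inputs.** Order S-R-R-R-S-S and 4 patients (Design & Procedures). Mean daily decrement 0.76, SD 0.16, target 0.62 %HbA/day (Background & Significance). Outcome interval from post-treatment k to pre-treatment k+1 (Data Analysis). Six treatments give 5 intervals if the last sample is at treatment 6. The documents do not say whether the interval after treatment 6 is measured, so results for 6 intervals follow in brackets.

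**The plan's own threshold.** Going from 30 to 37 days at a constant total loss needs a reduction of 1 - 30/37 = 18.9%, and 0.76 x 30/37 = 0.616, which rounds to 0.62. The stated 19% is reproduced. The target difference is 0.76 - 0.62 = 0.14 %HbA/day.

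**Estimability.** With patient effects, categorical interval and treatment, the design matrix has rank 8 for 9 columns (9 for 10). Adding treatment does not raise the rank, so R-S is not estimable.

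**Bias of the patient-plus-treatment model.** With no treatment effect, the estimate is the mean of the shared pattern over R intervals minus its mean over S intervals. R occupies intervals 2, 3, 4; S occupies 1, 5 (1, 5, 6). Loss is counted as positive, so a negative bias favours rejuvenation.

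| Shared pattern of size D | 5 intervals | 6 intervals |
|---|---|---|
| Linear drift, D per interval | 3 - 3 = 0 | 3 - 4 = -1.00D |
| First interval differs | 0 - 1/2 = -0.50D | 0 - 1/3 = -0.33D |
| Step after interval 1 | 1 - 1/2 = +0.50D | 1 - 2/3 = +0.33D |
| Step after interval 2 | 2/3 - 1/2 = +0.17D | 2/3 - 2/3 = 0 |
| Step after interval 3 | 1/3 - 1/2 = -0.17D | 1/3 - 2/3 = -0.33D |
| Step after interval 4 | 0 - 1/2 = -0.50D | 0 - 2/3 = -0.67D |
| Step after interval 5 | not applicable | 0 - 1/3 = -0.33D |

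**Size.** D is not in the documents. I assume 0.04 to 0.16 %HbA/day, a quarter of the stated SD up to the whole of it. For the first-interval and step patterns, the worst-case bias is 0.50 x 0.04 = 0.02 to 0.50 x 0.16 = 0.08, or 14 to 57% of 0.14. With 6 intervals it is 0.027 to 0.107, or 19 to 76%. To imitate the full target, D must be 0.14/0.50 = 0.28 (0.14/0.667 = 0.21), which nothing in the documents supports.

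**Modelling as a substitute.** A quadratic interval trend can be fitted, but it multiplies the variance of R-S by 21 (3.7).

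**Effect on a test.** In simulations with no treatment effect, a shared interval SD of 0.04 to 0.12 and a within-patient SD of 0.08 to 0.16 (all assumed), a two-sided 5% test of R-S = 0 without interval terms rejects in 7 to 29% of trials. This tests zero difference, not the plan's 19% rule.

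**Mirrored orders.** With 2 patients on S-R-R-R-S-S and 2 on R-S-S-S-R-R, patient plus categorical interval plus treatment has full rank, 9 (10). Every bias in the table becomes zero. The variance of R-S is 1/4.8 = 0.208 sigma² (1/6.0 = 0.167 sigma²), the same as for the single order without interval terms.

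**The case against.** The strongest reply is that no harm has been shown. The patients are already chronically transfused, their care pattern is recorded but not altered, and starting and ending on standard product cancels linear drift over 5 intervals. The text offers no mechanism for a special first interval or a step. The SD of 0.16 describes records from 15 patients, not shared interval effects, so the percentages rest on an assumed D. All of this stands, and it is why the bias is possible and not demonstrated.

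It also stands that only effects tied to treatment number are shared by design. Calendar effects line up only if patients enrol together, and enrolment timing is not stated. A step after interval 4 in a single patient gives 0.50D/4 = 0.125D (0.167D). At D = 0.16 that is 0.020 (0.027), or 14% (19%) of the target. Mirroring does not shrink that error; randomising only makes its sign random.

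The plan also calls itself a pilot without a control group, and estimating an effect size is ordinary pilot use. That sentence does not cure the problem: the same section goes on to compare rejuvenated with standard product and states a firm conclusion without carrying the limitation over. The missing storage-age and volume terms are incidental and do not carry the point.

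**Conclusion.** The concern holds, as something that should be changed. That all patients share one order, and that R-S is not estimable with free interval effects, follows from the text whether 5 or 6 intervals are observed. The size of any bias is conditional. It requires a non-linear effect shared by treatment number (with 6 intervals, linear drift also matters unless adjusted for), and the 14 to 57% (19 to 76%) range rests on the assumed D. The documents support neither a bias as large as the target nor the planned conclusion that rejuvenation itself permits a longer interval.

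**What to change.** **Preferred.** Randomise the 4 patients 2:2 to S-R-R-R-S-S or R-S-S-S-R-R, balance RBC-ST and RBC-XT across the orders where possible, and prespecify patient and categorical interval terms. This needs a four-line allocation list, with no added patients, treatments or procedures, and still 3 rejuvenated treatments each.

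The costs are these:
- Residual degrees of freedom fall from 15 to 11 (19 to 14). A 95% interval widens by 2.201/2.131 = 1.033, about 3.3% (2.145/2.093 = 1.025, 2.5%), at the same residual SD.
- Half the patients have no on-study standard interval first, and mirrored patients give 2 R and 3 S intervals if only 5 are observed.
- If the patients are 2 RBC-ST and 2 RBC-XT (assumed), unrestricted allocation puts each modality wholly in one order in 2 of 6 allocations. Modality-specific interval effects would then again be aliased with treatment, hence the balancing.
- Carry-over from a preceding rejuvenated treatment is not removed. For a carry-over of c per interval, the bias goes from +0.167c to -0.083c (+0.333c to +0.167c).

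**If enrolment has started.** Give the remaining patients the mirrored order and use categorical interval. A 3:1 split gives 0.278 (0.222) sigma² with no shared-interval bias. A linear term there would leave a first-interval bias of -0.25D (-0.24D). This allocation is not random, and a single mirrored patient cannot be balanced on modality.

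**If the order cannot change.** State that the design is single-sequence, and replace the conclusion about longer intervals with a hypothesis-generating within-patient difference that cannot be separated from shared interval effects. This costs only text. A linear interval term is then a sensitivity analysis. It changes no estimate with 5 intervals. With 6, it removes linear drift and cuts the step-after-4 bias from -0.67D to -0.48D, but raises the first-interval bias from -0.33D to -0.52D and the variance from 0.167 to 0.182 sigma².
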